## 9.9 Cancer Surgery, Therapy, and Radiotherapy

PC-related treatments that occur before and on study will be summarized for the Safety Analysis Set by visit and treatment type. The number of historical and on-study cancer therapies, radiotherapies, and surgeries will be summarized by visit and type of treatment.

Any cancer surgeries, therapies, and radiotherapies, including start and stop dates, treatment type, treatment regime, and response information will also be listed for each participant.

## 9.10 Conventional Imaging and Histopathology

Standard of care (SOC) conventional imaging will be performed during screening as part of eligibility into the trial and at Day 90 and 180 (if applicable) to establish the Reference Standard. Furthermore, additional SOC conventional imaging can be completed at investigator discretion within 180 days (±15 days) of Day 0. Both local and central reads of these scans will be summarized and listed.

September 4, 2024 CONFIDENTIAL Page 26 of 46

The type of imaging, modality of imaging, and recurrent PC status will be summarized as well as the results for each region and subregion, including evidence of lesions, equivocality, and number of lesions for the FAS

Similarly, local histopathology findings will be summarized for the FAS, including the type of histopathology procedure, scan type where the lesion was identified, imaging modality used to guide biopsy (if applicable), number of lesions biopsied, number of lesions per subject with histopathology, and results for the 5 anatomical regions (PC positivity, histologic type, Gleason Score, and Gleason Grade). Central histopathology results will be summarized from the expert reference panel CRF.

Local and central SOC conventional imaging results and histopathology findings will be listed for all participants for the Enrolled Analysis Set.

## 9.11 Study Drug Administration

Participants will receive a single dose of Cu-SAR-bisPSMA on Day 0. The following information will be summarized for the Safety analysis set:

- Make and model of dose calibrator.
- Reference vial activity.
- Activity in syringe before and after injection in MBq.
  - $\circ$  1 mCi = 37 MBq
- Method of administration.
- Number of participants with a complete dose administered and reasons for not completely administered doses.
- Actual administered activity of Cu-SAR-bisPSMA.

All Cu-SAR-bisPSMA administrations will be listed with complete information from the Cu-SAR-bisPSMA administration eCRF.

## 9.12 Cu-SAR-bisPSMA PET/CT Imaging

Cu-SAR-bisPSMA PET/CT imaging will be performed on Day 0 and Day 1. The scans will be assessed by a local reader and by three central readers.

For the local reader, the Cu-SAR-bisPSMA PET/CT results (at both timepoints), the evidence of Cu-SAR-bisPSMA uptake and number of lesions and any equivocal findings in each region/subregion will be summarized in the FAS.

September 4, 2024 CONFIDENTIAL Page 27 of 46

All Cu-SAR-bisPSMA PET/CT local reader data will be listed.

All central Cu-SAR-bisPSMA PET/CT imaging results, including status and number of unequivocal lesions, will be summarized at the region-level, subregion-level, and participant-level by central reader.

All Cu-SAR-bisPSMA PET/CT results (at both timepoints) for each central reader per participant at the subregion and region level, including lesion number, tumor state, sub-subregion, and reader comments on each lesion, will be listed.

#### 9.13 Reference Standard

The reference standard results, as defined in Section 7.7, for the region-level, subregion-level, and participant-level will be summarized, including the level of evidence used and details surrounding the imaging, histopathology, and confirmation of PSA results that go into the final reference standard result.

All reference standard results for each participant will be listed with information for imaging at the region-level, subregion-level, and participant level, histopathology at the region and participant-level, and confirmation of PSA results at the participant-level.

#### 9.14 Efficacy Analyses

All efficacy endpoints will be assessed using the FAS with supportive analyses performed with the PP analysis set for the primary efficacy endpoints and selected secondary endpoints. For definitions of Cu-SAR-bisPSMA PET/CT positive status criteria see Section 7.7 and for definitions of assessment of Cu-SAR-bisPSMA results against the Reference Standard results, see Section 7.8. Alpha level is set to 0.05 for all p-values but alpha is not controlled, and p-values are considered exploratory.

All analyses that are considered "region-level" will be conducted in 2 ways (unless otherwise specified): the analysis will be conducted on all 5 regions as a whole (labeled as "All Regions") and by-region individually, for 6 total calculations.

#### 9.14.1 Primary Efficacy Analyses

The co-primary efficacy endpoints are the following:

- Participant-level CDR at Day 0.
- Participant-level CDR at Day 1.
- Region-level PPV at Day 0.
- Region-level PPV at Day 1.

September 4, 2024 CONFIDENTIAL Page 28 of 46

 $\underline{CDR}$  on a participant-level for each central reader is defined as the proportion of TP participants out of all scanned participants who had at least 1 evaluable reference standard datapoint collected and is calculated as:  $\overline{CDR} = \overline{TP}/(all\ scanned\ participants\ with at least 1 evaluable reference datapoint) x 100.$ 

Participants without a Cu-SAR-bisPSMA PET/CT scan at the specific timepoint (Day 0 or Day 1) will be excluded from the participant-level CDR calculation for that timepoint. Participants with non-evaluable participant-level Reference Standard results will be excluded from the CDR calculation

PPV is measured on a region-level (the primary endpoint will be calculated including all 5 regions as a whole) for each central reader and is defined as the proportion of TP regions out of all positive regions on the  $^{64}$ Cu-SAR-bisPSMA PET/CT scan with corresponding evaluable composite Reference Standard data and will be calculated as: PPV = TP/(TP + FP) x 100, where FP = False Positive.

Regions that are not positive on the Cu-SAR-bisPSMA PET/CT scan at a specific timepoint will be excluded from the region-level PPV for that timepoint. PET/CT positive regions without corresponding evaluable composite Reference Standard results will also be excluded.

The anatomic regions for the PPV calculation are the following:

- Region 1 = Prostatic
- Region 2 = Pelvic lymph nodes
- Region 3 = Extra pelvic lymph nodes
- Region 4 = Visceral/soft tissue
  - o This region is incorrectly labeled as Region 5 in the raw data and will be recoded
- Region 5 = Bone
  - o This region is incorrectly labeled as Region 4 in the raw data and will be recoded

CDR and PPV will be summarized by central reader at Day 0 and Day 1 for participants who had at least 1 reference datapoint, and 2-sided 95% exact binomial confidence intervals (CI) using the Clopper-Pearson method. All primary endpoints will be summarized for the FAS (noting that subjects within the FAS without sufficient results to construct the required outcome variable for the endpoint [e.g. a participant without and evaluable reference datapoint cannot contribute to the determination of CDR] will by nature not be included in the respective endpoint analysis) and will be repeated in PP analysis set as supportive analyses.

Histogram panels will be presented displaying the participant-level CDR and region-level PPV by central reader at Day 0 and Day 1 in the FAS analysis set.

September 4, 2024 CONFIDENTIAL Page 29 of 46

## 9.14.1.1 Sensitivity Analysis for the Primary Endpoints

The following sensitivity analysis will be conducted on all participants in the FAS regardless of whether there are reference datapoints collected. Missing data will be handled in two different ways:

## • Worst-case Imputation:

- For the participant-level CDR on Day 0 and 1, participants with missing, non-evaluable, or inconclusive Reference Standard data will be imputed as non-TP and will be included in the denominator. The results will be presented in same way as the primary analysis for CDR.
- o For the region-level PPV on Day 0 and 1, PET/CT positive regions with missing, non-evaluable, or inconclusive Reference Standard data will be imputed as FP. The results will be presented in same way as the primary analysis for PPV.

## • Tipping Point Analysis:

- A tipping point analysis will be performed for both participant-level CDR and region-level PPV, where participants with missing or non-evaluable Reference Standard data will be imputed as TP with probability *p* ranging from 0 to 1 with an increment of 0.1.
- o p = 0 corresponds to none of the participants in the Reference Standard with missing data will be imputed as TP while p = 1 corresponds to all participants in the Reference Standard with missing data will be imputed as TP.
- For each of the 11 values of *p* (0-1 by 0.1), 20 imputation datasets will be constructed and combined, where the value of *p* is the probability that the imputation will be TP. The results will be presented in same way as the primary analysis for CDR and PPV for Day 0 and 1 without 95% CI.
- Figures displaying the CDR or PPV curve of point estimates for each value of *p* will be presented.

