 - For the region-level PPV calculation on Day 0 and on Day 1 based on FAS, PET/CT positive regions with missing/non-evaluable corresponding composite Reference Standard data will be imputed as FP and included in the denominator.
 - Tipping Point Analysis:
 - In addition, to examine the impact of missing or non-evaluable composite Reference Standard data and evaluate the robustness of the results, a tipping point analysis will be performed as a sensitivity analysis for participantlevel CDR and region-level PPV based on the FAS, where participants with missing or non-evaluable composite Reference Standard data will be imputed as TP with probability of p ranging from 0 to 1 with an increment of 0.1 (p = 0 corresponds to none of the participants without Reference Standard information in a PET positive region will be imputed as true positive while p = 1 means all participants without Reference Standard information in a PET positive regions will be imputed as TP).

Details of handling of missing data will be fully described in the SAP.

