## • True Positive:

- Histopathology: A region that is Cu-SAR-bisPSMA PET-positive (includes at least one unequivocal PET-positive lesion) and Reference Standard positive is considered a TP region.
- o Imaging: A subregion that is Cu-SAR-bisPSMA PET-positive (i.e., includes at least one unequivocal PET-positive lesion) and Reference Standard positive (i.e., includes at least one unequivocal lesion detected on conventional imaging in that subregion) is considered a TP subregion. The subregion must match between the two assessments. If any region has at least one TP subregion, the region-level status is considered TP.

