## • Non-evaluable:

o A region that has either non-evaluable (NE) Cu-SAR-bisPSMA PET/CT results for a specific timepoint (Day 0 or Day 1) or has a non-evaluable or inconclusive Reference Standard will not be assigned for that timepoint.

Assessments of **Participant-Level** Reference Standard against the Cu-SAR-bisPSMA PET/CT results:

• True Positive:

September 4, 2024 CONFIDENTIAL Page 22 of 46

- A participant with at least one TP region and/or at least one unequivocal Cu-SAR-bisPSMA positive lesion in any region and a confirmed PSA response to radiation or other salvage focal therapy.
  - Confirmed PSA response following radiation or other salvage focal therapy (as long as no concomitant ADT is given) = total PSA decline ≥50% from baseline, confirmed by a 2nd value within 4 weeks per Prostate Cancer Working Group 3 criteria.

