#### 8.0 DEVIATIONS FROM PROTOCOL ANALYSES

**Table 3** Deviations from Protocol Analyses

Analysis Endpoint and SAP Section	Protocol v3.0 Original Analysis	Updated Analysis	Rationale
Exploratory Outcome: Function of Baseline	This analysis includes Lesion-to-background ratio as per protocol.	Lesion-to-background ratio not included in this exploratory analysis.	Inclusion of lesion-to- background ratio is not deemed necessary or
Variables Section 9.14.3.2.			informative in this analysis.

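### The SAP's tipping-point analysis does not limit imputation to PET-positive participants, so its CDR curve can run past what is attainable, and it drops the confidence bound that would show where CDR or PPV tips

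*SAP*

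**What the plan says.** SAP 9.14.1.1 runs its sensitivity analyses on the whole FAS, whether or not reference data were collected. In the tipping-point part, participants with missing or non-evaluable reference data become true positive (TP) with probability p, from 0 to 1 in steps of 0.1, using 20 imputed datasets per step. The upper end is defined as "p = 1 corresponds to all participants in the Reference Standard with missing data will be imputed as TP". On output it says "The results will be presented in same way as the primary analysis for CDR and PPV for Day 0 and 1 without 95% CI", and the figures plot point estimates.

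Protocol 10.4.5.1 opens as broadly: "participants with missing or non-evaluable composite Reference Standard data will be imputed as TP with probability of p ranging from 0 to 1". Its explanation of the end points is narrower, however: at p = 1, "all participants without Reference Standard information in a PET positive regions will be imputed as TP".

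SAP 7.8 defines a TP. For histopathology, a region that "includes at least one unequivocal PET-positive lesion) and Reference Standard positive is considered a TP region". The imaging route requires a matching PET-positive subregion. A participant needs a TP region, or a PET-"positive lesion in any region and a confirmed PSA response to radiation or other salvage focal therapy".

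The worst-case analysis in the same SAP section covers one more category: "participants with missing, non-evaluable, or inconclusive Reference Standard data will be imputed as non-TP and will be included in the denominator". It is presented like the primary analysis, so with an exact interval.

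The only entry in SAP Table 3 (deviations from protocol analyses) is "Lesion-to-background ratio not included in this exploratory analysis".

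**The concern.** There are two separate problems.

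**CDR only.** A PET-negative participant cannot be a TP, whatever the reference would have shown. The SAP rule nevertheless converts such a participant with probability p, and with certainty at p = 1. The protocol's explanation of p excludes this; the SAP leaves the limit out, and Table 3 does not record the difference. Region-level PPV is not affected, because only PET-positive regions enter it.

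**CDR and PPV.** A tipping-point analysis should show how favourable the missing outcomes must be for a conclusion to change. The only numerical targets in the plan are the lower exact 95% bounds in the sample-size sections (Protocol 10.3, SAP 4.2), and no other definition of a tip is given. A curve of point estimates does not show where a lower bound passes its target. The worst-case analysis gives an interval only at the p = 0 end.

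The stake is how robustness is read. The primary analysis excludes participants without an evaluable reference, and the plan allows for 20% non-evaluable. If the primary bound clears its target and the worst case does not, the reader needs the crossing point and would have to compute it outside the planned output.

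**Working it through.** **Inputs (SAP 4.2).** CDR 42%, 40 evaluable, 20% non-evaluable, about 50 scanned, target lower bound above 20%. PPV 65%, about 34 positive regions (40 × 0.65 × 1.3 = 33.8), target lower bound above 40%. PET-positive share 65%.

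**Assumptions added here.** All 10 of the planned non-evaluable participants lack reference data. Their PET-positive share is 65%, varied from 40% to 90%. Missing positive regions: 10 × 0.65 × 1.3 = 8.45, taken as 8. Regions are treated as independent, as the plan does.

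**Step 1: reproduce the plan.** The Clopper-Pearson lower bound for x of n is the 2.5% quantile of Beta(x, n − x + 1).
- CDR: the smallest passing count is 14/40 (20.6%). P(X ≥ 14) for Binomial(40, 0.42) is 85.5%; the plan says more than 85%.
- PPV: the smallest passing count is 20/34 (40.7%). P(X ≥ 20) for Binomial(34, 0.65) is 82.6%; the plan says more than 80%.

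**Step 2: ceiling of the CDR curve at p = 1.**
- SAP text: (0.42 × 40 + 10)/50 = 26.8/50 = 53.6%.
- Attainable, with a share s of the 10 PET-positive: (16.8 + 10s)/50.

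| s | Attainable maximum | Excess of SAP curve |
|---|---|---|
| 0.40 | 41.6% | 12 points |
| 0.65 | 46.6% | 7 points |
| 0.90 | 51.6% | 2 points |
| 1.00 | 53.6% | 0 |

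With 5 missing (45 in total) and s = 0.65, the excess is 5 × 0.35/45 = 3.9 points.

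**Step 3: where the bound crosses.**

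| Endpoint | Case | TP/n | Estimate | Lower bound |
|---|---|---|---|---|
| CDR | primary | 14/40 | 35.0% | 20.6% |
| CDR | worst case | 14/50 | 28.0% | 16.2% |
| CDR | +2 TP | 16/50 | 32.0% | 19.5% |
| CDR | +3 TP | 17/50 | 34.0% | 21.2% |
| PPV | primary | 22/34 | 64.7% | 46.5% |
| PPV | worst case | 22/42 | 52.4% | 36.4% |
| PPV | +1 TP | 23/42 | 54.8% | 38.7% |
| PPV | +2 TP | 24/42 | 57.1% | 41.0% |

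In the CDR example, three imputed TPs are needed. That is p = 3/10 = 0.3 under the SAP text, but 3/7 = 0.43 to 3/6 = 0.50 if 7 or 6 of the 10 are PET-positive. In the PPV example, two are needed: p = 2/8 = 0.25. The planned point-estimate curves start at 28.0% and 52.4%, already above 20% and 40%, so they never meet the targets.

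**Step 4: how often the primary bound passes and the worst-case bound fails.**

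| Endpoint | Missing | TP counts | Probability |
|---|---|---|---|
| CDR, Binomial(40, 0.42) | 10 | 14–16 | 32% |
| | 8 | 14–15 | 20% |
| | 5 | 14 | 9% |
| PPV, Binomial(34, 0.65) | 8 regions | 20–23 | 51% |
| | 6 regions | 20–22 | 38% |
| | 4 regions | 20–21 | 23% |

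**The case against.** **The PET-positive limit can be inferred.** The protocol's opening sentence is as broad as the SAP's, the TP definition rules out a PET-negative TP, and the programming supplement cited in SAP 7.8 was not available for this review. A careful programmer might apply the limit anyway. That is why the claim is only that the curve can exceed the maximum. But the SAP's wording is that all such participants are imputed, and a prespecified analysis should not depend on someone overriding it.

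**The excess sits at the upper end, while robustness is judged near the lower end.** This is partly right: the number of imputed TPs needed is the same under either rule. The p attached to that number does move, from 0.3 to between 0.43 and 0.50 in the CDR example.

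**No formal test is planned, and 20% and 40% are planning targets.** This stands. SAP 4.1 is explicit, neither document promises an interval at each p, and pooling 20 datasets would need a combining rule. So no decision rule is broken. The primary and secondary analyses also report exact intervals without a test, and a bound tabulated by number of imputed TPs needs no pooling. A reader could work the bound out by hand, but the planned output would not show it.

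**The missingness may be milder.** Follow-up imaging is required of everyone, and incomplete participants may be replaced. At 17/40, close to the planned 42%, the worst case 17/50 already has a bound of 21.2%, so CDR does not tip. The sizes do depend on how many are missing, as steps 2 and 4 show.

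**Conclusion.** The concern holds on both parts.

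Followed as written, the SAP gives unattainable CDR values at the upper end of the curve whenever any participant without reference data is PET-negative. The excess is 7 points at the planning values and 2 to 12 points for PET-positive shares of 90% to 40%, given 10 of 50 missing. It vanishes only if all the missing are PET-positive.

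For both endpoints, the planned output cannot show where the lower bound crosses its target. Under the plan's assumptions, a crossing between worst case and primary has probability 32% for CDR and 51% for PPV at the full non-evaluable allowance, and 9% and 23% with 5 participants or 4 regions missing. These figures rest on planning values, not data.

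The effect is confined to the robustness output. It should be corrected, but the primary and worst-case analyses stand.

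**What to change.** Amend the tipping-point text in SAP 9.14.1.1, for each reader and timepoint, as follows.

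- Impute TP with probability p only for PET-positive participants (CDR) or PET-positive regions (PPV) that lack an evaluable reference. Keep PET-negative participants without a reference in the CDR denominator as non-TP at every p.
- Cover missing, non-evaluable and inconclusive references, as the worst-case analysis does. The current tipping-point text omits inconclusive results, so p = 0 need not reproduce the worst case.
- Report the exact 95% lower bound by number of imputed TPs, or at each p, with the smallest value at which it exceeds 20% (CDR) or 40% (PPV). Label this descriptive, since no formal test is planned.

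The cost is a few sentences in the SAP and a small program change. No new data are needed.

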## 9.14.2 Secondary Efficacy Analyses

The following secondary analyses will be performed in a similar manner as the primary analysis, and will be summarized by central reader with point estimates and exact Clopper-Pearson 95% CI in the FAS and repeated with the PP analysis set:

- Participant-level PPV at Day 0 and Day 1;
  - $\circ$  PPV = TP/(TP + FP) x 100.
- Participant-level Detection Rate (DR) at Day 0 and Day 1;
  - o DR = (number of participants with positive Cu-SAR-bisPSMA PET/CT scan)/(all scanned participants with a Cu-SAR-bisPSMA PET/CT scan) x 100.

September 4, 2024 CONFIDENTIAL Page 30 of 46

- Participant-level False Positive Rate (FPR) on Day 0 and Day 1;
  - $\circ$  FPR = FP/(all scanned participants with a positive Cu-SAR-bisPSMA PET/CT scan and an evaluable reference standard) x 100.
- Region-level FPR at Day 0 and Day 1;
  - $\circ$  FPR = FP regions/(all positive regions on the Cu-SAR-bisPSMA PET/CT scan and an evaluable reference standard) x 100.
- Participant-level discrepant PET negative rate between Day 0 and Day 1 for reference standard positive participants.
- Discrepant PET negative rate;
  - O Discrepant PET negative rate = (number of participants with participant-level discrepancy in Cu-SAR-bisPSMA results between Day 0 and 1) / (all participants with a positive reference standard) x 100.
- Participant-level True Negative Rate (TNR) on Day 0 and Day 1;
  - $\circ$  TNR = TN/(TN+FP) x 100.
- Participant-level Apparent Negative Predictive Value (ANPV; referred to as TNR in the study protocol) on Day 0 and Day 1;
  - o TN/(number of participants with a negative Cu-SAR-bisPSMA result)
- Region-level TNR at Day 0 and Day 1.
  - $\circ$  TNR = TN/(TN+FP) x 100.
- Region-level Apparent Negative Predictive Value (ANPV; referred to as TNR in protocol) at Day 0 and Day 1;
  - o TN/(number of regions with a negative Cu-SAR-bisPSMA result).

Note: Discrepant Day 0 and Day 1  $^{64}$ Cu-SAR-bisPSMA PET/CT results (results differ within subregion from Day 0 and Day 1 within the same central reader) will also be listed.

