2.7.2 Secondary Objectives and Endpoints

The secondary study objectives and endpoints to be evaluated in this study are presented in Table 2.

Fable 2 Secondary Study	Objectives	and Endpoints
--------------------------------	-------------------	---------------

Objective	Endpoint	
To investigate the biodistribution of ⁶⁴ Cu-SAR-bisPSMA.	Biodistribution of ⁶⁴ Cu-SAR-bisPSMA on the Day 0 and Day 1 scan:	
	• Maximum and mean SUVs in lesion(s), visceral/soft tissue, bone.	
	Lesion-to-background ratio.	
To assess the participant-level PPV of ⁶⁴ Cu-SAR-bisPSMA PET/CT.	• Participant-level PPV, defined as the proportion of TP participants on the Day 0 scan out of all participants with a positive Day 0 scan.	
	• Participant-level PPV, defined as the proportion of TP participants on the Day 1 scan out of all participants with a positive Day 1 scan.	
To assess the participant-level DR of ⁶⁴ Cu-SAR-bisPSMA PET/CT.	• Participant-level DR, defined as the proportion of participants with a positive Day 0 scan out of all participants with a Day 0 scan.	
	• Participant-level DR, defined as the proportion of participants with a positive Day 1 scan out of all participants with a Day 1 scan.	

To assess the FPR ⁶⁴ Cu-SAR- bisPSMA PET/CT.	• Participant-level FPR, defined as the proportion of FP participants on the Day 0 scan out of all participants with a positive Day 0 scan.
	• Participant-level FPR, defined as the proportion of FP participants on the Day 1 scan out of all participants with a positive Day 1 scan.
	• Region-level FPR, defined as the proportion of FP regions on the Day 0 scan out of all positive regions on the Day 0 scan.
	• Region-level FPR, defined as the proportion of FP regions on the Day 1 scan out of all positive regions on the Day 1 scan.
To assess the rate of discrepant PET negativity rate of the ⁶⁴ Cu-SAR-bisPSMA PET/CT scans.	Participant-level discrepant PET negativity rate, defined as the proportion of participants with contradicting Day 0 and Day 1 results for whom the Reference Standard was positive.
To assess the TNR of ⁶⁴ Cu-SAR- bisPSMA PET/CT.	• Participant-level TNR, defined as the proportion of TN participants on the Day 0 scan out of all participants with a negative Day 0 scan.
	• Participant-level TNR, defined as the proportion of TN participants on the Day 1 scan out of all participants with a negative Day 1 scan.
	• Region-level TNR, defined as the proportion of TN regions on the Day 0 scan out of all negative regions on the Day 0 scan.

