10.4.5.2 Secondary Efficacy Analyses

Secondary efficacy endpoints include the following:

- Participant-level PPV on Day 0 and on Day 1;
- Participant-level DR on Day 0 and on Day 1;
- Participant-level FPR on Day 0 and on Day 1;
- Region-level FPR on Day 0 and on Day 1;
- Participant-level discrepant PET negative rate between Day 0 and Day 1;
- Participant-level TNR on Day 0 and on Day 1;
- Region-level TNR on Day 0 and on Day 1.

Secondary efficacy endpoints will be analyzed on the FAS. Point estimates and 2-sided 95% exact binomial CIs will be presented for each central reviewer separately.

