#### 6.0 ANALYSIS SETS

For the purposes of defining the analysis sets, a participant is considered enrolled when they have a Day 0 visit. Unless otherwise specified, data for participants who were enrolled but did not receive a Cu-SAR-bisPSMA administration will be listed but will not be included in summary tables. For purposes of analysis, the following analysis sets are defined:

Table 1 Analysis Sets

Analysis Set	Description	
All Participants Set	All screened participants who signed the informed consent form. Screen failure information will be summarized using the All Participants Set.	
Enrolled Analysis Set	All participants who signed the informed consent form (ICF) and were enrolled into the study. This will be used for patient disposition and analysis set summaries.	
Safety Analysis Set	All enrolled participants who receive any amount of  Cu-SAR-bisPSMA. This will be used to assess safety data.	
Full Analysis Set (FAS)	All participants who receive any amount of  Cu-SAR-bisPSMA and have  Cu-SAR-bisPSMA PET/CT imaging results from at least one central reader. This will be used for all efficacy analyses.	
Per Protocol (PP) Analysis Set	All participants in the FAS who have an evaluable assessment of the Reference standard against  Cu-SAR-bisPSMA PET/CT imaging results for the participant-level and at least 1 region for the Day 0 and Day 1  Cu-SAR-bisPSMA PET/CT scan and who	

September 4, 2024 CONFIDENTIAL Page 15 of 46

	have no exclusionary protocol deviations that exclude them from PP analysis. Participants that were replaced on study will not be included. This will be used to repeat the primary and selected secondary efficacy analyses only.
Biodistribution Analysis Set	All participants in the Safety Analysis Set who have at least one biodistribution measure. This will be used to summarize biodistribution data.

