## 7.3 Handling of Missing Data

- Missing values for individual data points will remain as missing. Missing values will not be imputed and only observed values will be used in data analyses and presentations unless otherwise indicated. For the reference standard, expert panel adjudications will never be missing and will be assigned as "non-evaluable" if based on missing data. Sensitivity analyses will be performed for non-evaluable reference standard assessments.
- Where individual data points are missing, categorical data will be summarized based on reduced denominators (i.e., only patients with available data will be included in the denominators) unless otherwise indicated.

September 4, 2024 CONFIDENTIAL Page 17 of 46

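### Region-level ANPV: the denominator as written includes regions that cannot be true negatives, and the pooled confidence interval ignores clustering within participants

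*SAP*

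**What the plan says.** For every region-level endpoint, SAP 9.14 states that "the analysis will be conducted on all 5 regions as a whole", and that each region is also analysed alone. SAP 9.14.2 then has the secondary endpoints "summarized by central reader with point estimates and exact Clopper-Pearson 95% CI". Protocol 10.4.5.2 agrees: "2-sided 95% exact binomial CIs will be presented for each central reviewer separately". Neither document adjusts for several regions coming from one participant.

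The denominators in SAP 9.14.2 differ:

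- Region-level ANPV, which the SAP identifies as the protocol's TNR, is "TN/(number of regions with a negative" PET result. No condition is placed on the reference standard. Participant-level ANPV has the same form.
- FPR, in the same list, requires a positive "PET/CT scan and an evaluable reference standard".
- TNR in the SAP's own sense is TN/(TN+FP), so unassigned regions drop out automatically.
- The co-primary PPV (SAP 9.14.1) excludes positive regions that lack an evaluable reference standard.

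The protocol's objective table has "Region-level TNR, defined as the proportion of TN regions on the Day 0 scan out of all negative regions on the Day 0 scan".

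Three other passages bear on this. SAP 7.8 gives no TP, FP or TN status to a region whose reference standard is non-evaluable or inconclusive. The FAS asks only for dosing and "PET/CT imaging results from at least one central reader". SAP 7.3 says that "expert panel adjudications will never be missing and will be assigned as" non-evaluable when they rest on missing data.

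**The concern.** There are two separate faults.

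**Denominator.** A PET-negative region without an evaluable reference standard can never enter the numerator, but the formula as written leaves it in the denominator. It then counts as though the scan had failed, which pulls ANPV down. If a participant has no reference data at all, his four or so PET-negative regions become non-TN together, which makes regions within a participant strongly alike. The reduced-denominator rule in SAP 7.3 does not clearly remove them, because it concerns missing data points and the same section says an adjudication is never missing.

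**Interval.** Clopper-Pearson assumes independent units. Pooling five regions per man breaks that assumption under either reading of the denominator. If regions within a man tend to agree, the interval is too narrow.

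At stake is the accuracy and stated precision of one pooled secondary estimate, reported for each reader and each scan day. SAP 4.1 plans no formal testing, so no decision rule depends on it. Protocol 7.5.2 already warns that the design cannot assess false negatives reliably, so a biased or falsely precise measure on the negative side is unhelpful.

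**Working it through.** **Plan's own figures first** (Protocol 10.3, SAP 4.2). All reproduce.

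- Positive regions: 40 × 0.65 × 1.3 = 33.8, about 34.
- PPV: at least 20 of 34 are needed for the exact lower limit to exceed 40%; power at 65% is 82.6% (stated: more than 80%).
- CDR: at least 14 of 40 are needed to exceed 20%; power at 42% is 85.5% (stated: more than 85%).
- Enrolment: 40 / 0.8 = 50.

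Neither document gives a precision figure for ANPV.

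**Cluster size.** 40 × 5 = 200 regions, less 33.8 positive, leaves 166.2 PET-negative: 166.2 / 40 = 4.155 per participant, or about 208 among 50 scanned.

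**Literal denominator.** Let q be the share of participants wholly non-evaluable and p the true ANPV among evaluable regions, with evaluable regions independent.

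- Expected literal ANPV = (1 − q) × p
- Induced ICC = q × p / [1 − (1 − q) × p]
- Design effect (DE) = 1 + (4.155 − 1) × ICC

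The plan's non-evaluable rate is 20% but is not split by cause, so q is assumed. The first three result columns use p = 90%.

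| q | Literal ANPV | ICC | DE | Clopper-Pearson coverage, p = 85–95% |
|---|---|---|---|---|
| 20% | 0.80 × 0.90 = 72% | 0.18/0.28 = 0.64 | 3.03 | 71–78% |
| 10% | 0.90 × 0.90 = 81% | 0.09/0.19 = 0.47 | 2.49 | 75–83% |
| 5% | 0.95 × 0.90 = 85.5% | 0.045/0.145 = 0.31 | 1.98 | 80–88% |

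The last column is simulated with 50 participants. It is coverage of the shifted quantity (1 − q) × p, not of p. Against p itself the bias dominates. At q = 20% and p = 90%, Clopper-Pearson contains 90% in 0.4% of simulated trials and a participant-clustered interval in only 1.5%; at q = 10% the clustered interval contains it in 28%. A wider interval does not repair the denominator.

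Illustration with p = 95% and q = 20%: 158/208 = 76%, exact CI 69.6–81.6%. The same data over evaluable regions give 158/166 = 95%, exact CI 90.7–97.9%.

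**Evaluable regions only.** Assumed: 40 participants; 1, 2 or 3 positive regions among PET-positive men with probability 0.75, 0.20 and 0.05 (mean 1.3); true ANPV 80–95% in the equal-rate case. Clopper-Pearson coverage (40,000 runs for equal rates, 20,000 for unequal):

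| ICC (assumed) | Equal rates across regions | Unequal rates |
|---|---|---|
| 0.05 | 94–96% | 95–96% |
| 0.1 | 93–94% | 94–95% |
| 0.2 | 89–91% | 91–93% |
| 0.3 | 86–88% | 88–91% |

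An interval from a robust variance clustered on participant, on the logit scale, covers 93–96% in these cases.

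**Other pooled measures.** PPV coverage is 96.7%, 95.8% and 94.4% at ICC 0, 0.2 and 0.4, because 34 regions come from about 26 participants. TNR coverage is 95–97% at ICC 0–0.6. Only extreme assumptions lower these materially, such as identical TP/FP status within a participant or a few men with all five regions positive.

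**The case against.** The strongest objection is that the literal denominator is not what the SAP means. SAP 9.14.2 introduces the secondary analyses as following the primary approach. SAP 9.14.1 excludes regions without an evaluable reference standard and adds that FAS participants whose outcome cannot be constructed drop out of that endpoint. The sentence in SAP 7.3 concerns panel adjudication, not TP/FP/TN status. The protocol's objective table does not settle it either: it also writes CDR, PPV and FPR without an evaluability condition, and the analysis sections then add one. All of this stands. What also stands is that FPR repeats the condition in the same list while ANPV omits it, so two programmers could reach different results.

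Second, the per-protocol repeat requires an evaluable participant-level assessment and at least one evaluable region on both days, which removes most of the denominator problem. That is correct, but the FAS is the main set, and ordinary clustering remains in both sets.

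Third, non-evaluability need not affect a whole participant. The protocol's example, a participant with no follow-up assessments, is of that kind, but an inconclusive result can belong to one region. The bias figures are therefore conditional on q.

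Fourth, with evaluable regions only, coverage is close to nominal up to ICC 0.1, and no document supports 0.2 or 0.3. That limits how serious the interval problem can be said to be.

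A reader might infer that the plan's nominal 95% interval really covers only 71–88%. The documents do not support that as a general statement: it needs the literal denominator and the assumed shares of wholly non-evaluable participants.

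**Conclusion.** The point holds as a wording gap with a possible bias, plus an interval that ignores clustering.

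- Read literally in the FAS, region-level ANPV is biased downward: a true 90% reads about 72%, 81% or 86% if 20%, 10% or 5% of participants are wholly non-evaluable. If the exclusion is intended, this bias disappears.
- Under either reading, the pooled Clopper-Pearson interval treats about 4.2 PET-negative regions per participant as independent. With evaluable regions only, the loss of coverage is negligible at ICC up to 0.1 and moderate at 0.2–0.3. The true ICC is unknown.

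The consequence is limited to a secondary, descriptive estimate. Single-region and participant-level intervals have one unit per participant, so clustering does not affect them, although the ANPV denominator question applies to them too.

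A reader might also infer that the co-primary PPV interval, or its stated power, is undermined. It is not: PPV coverage stays near nominal at plausible correlations, and the stated power of more than 80% reproduces at 82.6% for 34 regions.

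**What to change.** In SAP 9.14.2:

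1. Define the ANPV denominator, at participant and region level, as PET-negative units with an evaluable reference standard (those classed as TN or test-negative under SAP 7.8). This matches FPR and PPV. Report the number of PET-negative units excluded.
2. For the pooled All Regions ANPV, report a 95% CI clustered on participant, using a robust variance on the logit scale. Use Clopper-Pearson if the numerator is 0 or equals the denominator.

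Keep Clopper-Pearson everywhere else, including pooled PPV, FPR and TNR.

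The cost is SAP wording and a standard procedure, with no extra participants. The pooled ANPV interval becomes somewhat wider: at a true 85% with evaluable regions only, its average width goes from 0.113 to 0.125, 0.140 and 0.153 at ICC 0.1, 0.2 and 0.3. The first change is needed whether or not the second is made, since a clustered interval around the literal estimate would still be centred in the wrong place.
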